# 8.3 Sample Size and Power Determination

Sample size was calculated in STATA using the change in VAS needed for clinical significance, in concordance with effect sizes and standard deviations from previous studies. Sample size calculated to detect a clinically significant difference at each of three locations with alpha = 0.05 and a power of 0.8.

# 8.4 Statistical Methods

Quantitative VAS data will be analyzed by a two-tailed t-test, and by linear regression model, incorporating location, and order of intervention (i.e. intervention first or second). Quantitative preferential data will be analyzed by logistic regression model incorporating location and order of intervention.

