# 3.1.2 Study Intervention Phase

1. The study will take place in an examination room in the Dermatologic Surgery clinic at the Perelman Center for Advanced Medicine.

2. The KAD used will be the Blaine Labs Vibration Anesthesia Device. The device will be purchased from Blaine Labs directly.

3. Injections will be made up of 0.5mL of room temperature 1% lidocaine buffered with 8.4% sodium bicarbonate, procured from the dermatologic surgery clinic. Injections will use the standard syringe with 30 gauge needle.

4. Before any procedure is done or information is collected for the study, subjects will be asked to read and sign the consent form. Adequate time will be given for subjects to review the Informed Consent Document and review any of their questions or concerns with the study staff or Principal Investigator.

5. Baseline vital signs (heart rate and blood pressure) will be obtained prior to the first injection.

6. Then each subject will be randomized to one location: nasofacial sulcus, lateral forehead or lateral back.

7. Each subject will be randomized to receive the intervention with KAD either first or second.

8. The first injection will always be on the left side and the second will always be on the right

9. When the KAD is used for the injection, it will be held by the person giving the injection in their off hand. It will be firmly pressed on the skin, turned on, adjacent to the injection 1-2 seconds before the injection is given. The injection will be given into the lighted target area of the KAD. The device will be removed 1-2 seconds after the needle is withdrawn.

10. Each injection will be given in accordance with the current standard of practice. Injections will be given using the formulation and needle noted above. Injections will be given with the needle held perpendicular to the skin. The speed of the injection will be slow, aiming for 5 seconds to empty the syringe. All injections will be performed by [name], with verbal cues standardized.

11. After each injection, study participants will be asked to document their level of acute pain using the VAS. A paper and pen version of the scale will be used.

12. After both injections are complete, safety vitals will again be obtained (heart rate, blood pressure) in order to assess whether subject has tolerated the injection without any adverse reactions. If necessary, repeat vitals will be obtained until the Principal Investigator feels the subject is medically clear to leave.

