# 3.1.3 Allocation to Interventional Group

Participants will be randomized to one of three locations: nasofacial sulcus, lateral forehead, or upper back. Additionally, subjects will be randomized to receive the intervention with vibration anesthesia device on their first (left) or second (right)-sided injection. This is a split body study so each participant will receive 2 total injections – one with and one without the intervention. Randomization will be achieved by the selection of a sealed envelope by each study participant, that will have a location and an order listed. This will randomize subjects and will ensure that groups can be balanced, by creating equal numbers of envelopes for each of the groups.

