### 4.6 Total Number of Subjects and Sites

50 subjects enrolled for the study taking place at one site – Perelman Center for Advanced Medicine.

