# 8.2 Secondary Endpoints

Following the completion of both injections, volunteers will indicate which injection they preferred, with a no preference option included. Patients will also be queried on demographic information after the injections have been completed. They will be asked age, sex, role at University of Pennsylvania. Because pain is characterized as quantitative AND qualitative, include a free response section for comments, specifically asking Do you have any comments on how the kinetic anesthesia device affected your injection experience? A second qualitative entry section will ask: Were you bothered in any way by the VAD [check yes or no] if so please comment. Quantitative VAS data will be analyzed by a two-tailed ttest, and by linear regression model, incorporating location, and order of intervention (i.e. intervention first or second). Quantitative preferential data will be analyzed by logistic regression model incorporating location and order of intervention.

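### Preference is modelled by logistic regression on site and order in 50 people, with no method named for a site or order group that answers unanimously

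*Combined protocol and SAP*

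**What the plan says.** - **Model.** Section 8.4 states: "Quantitative preferential data will be analyzed by logistic regression model incorporating location and order of intervention". Section 8.2 and the Study Summary repeat it. No estimator, test, interval method or fallback is named.
- **Outcome.** Under section 8.2, "volunteers will indicate which injection they preferred, with a no preference option included". Section 2.2 lists the three answers: with the device, without it, or no preference. No section says how three answers become the outcome of a logistic model.
- **Size and groups.** Section 4.6 gives "50 subjects enrolled for the study taking place at one site". Section 3.1.3 says "Participants will be randomized to one of three locations: nasofacial sulcus, lateral forehead, or upper back", and section 3.1.2 says "Each subject will be randomized to receive the intervention with KAD either first or second". The sealed envelopes are meant to "ensure that groups can be balanced, by creating equal numbers of envelopes for each of the groups".
- **Sample size basis.** Section 8.3 refers only to the pain score (VAS): "Sample size calculated to detect a clinically significant difference at each of three locations with alpha = 0.05 and a power of 0.8". No preference rate is assumed anywhere.

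**The concern.** Unqualified logistic regression is normally read as maximum likelihood. That estimator needs both answers to occur in every site and in each order group. If one group is unanimous the data are separated: the fitted log-odds for that group runs to infinity, and so does every contrast that uses the group. If the unanimous site is the reference level, both location coefficients are affected. Software then typically prints a huge estimate with a huge standard error, or drops the site.

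At stake are the location and order effects on preference, which are what the specified model adds to a simple count. Without a rule set in advance, the team would choose a remedy (drop a site, merge sites, change the model) after seeing the answers. The risk grows as preference for KAD becomes stronger.

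**Working it through.** **Plan's own figure.** There is none for preference. The only size figure is 50. It rests on VAS, and no standard deviation is given, so it cannot be reproduced and says nothing about the preference model.

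**Inputs from the documents.** N = 50 (section 4.6); three sites, two orders and equal allocation (sections 3.1.2 and 3.1.3); main effects of location and order (section 8.4). The model has four coefficients: an intercept, two for location and one for order.

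**Assumptions.** Since 50 is not divisible by six, the cells are taken as 9, 8, 8, 8, 8, 9. This gives sites of 17, 16 and 17 and order groups of 25 and 25. The answer is treated as binary, with a true share p preferring KAD. The documents give no p, so a range is shown.

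**Step 1: unanimous groups.** Ignoring the negligible chance that a whole group prefers no device:

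- P(some site unanimous) = 1 − (1 − p^17)² (1 − p^16)
- P(some order group unanimous) = 1 − (1 − p^25)²

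At p = 0.80: 0.80^17 = 0.0225, 0.80^16 = 0.0281 and 0.80^25 = 0.0038. The site risk is 1 − 0.9775² × 0.9719 = 0.071, and the order risk is 1 − 0.9962² = 0.008.

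At p = 0.90: 0.90^17 = 0.167, 0.90^16 = 0.185 and 0.90^25 = 0.072. The site risk is 1 − 0.833² × 0.815 = 0.434, and the order risk is 1 − 0.928² = 0.138.

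The two events overlap, so they cannot simply be added.

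**Step 2: any separation.** Each cell can be all KAD, none KAD or mixed, which gives 3^6 patterns. Each pattern was tested for complete or quasi-complete separation by linear programming and weighted by its exact probability. To the accuracy shown, separation coincides with a unanimous site or order group. The 40-analysed row uses cells 7, 7, 7, 7, 6, 6, as if 20% answered no preference and were dropped.

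| True p | 70% | 75% | 80% | 85% | 90% | 95% |
|---|---|---|---|---|---|---|
| All 50 analysed | 0.8% | 2.6% | 7.6% | 20% | 46% | 83% |
| 40 analysed | 2.8% | 7.0% | 16% | 33% | 60% | 90% |

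The risk passes 50% at p of about 90.5% with 50 analysed, and about 88% with 40.

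**Step 3: sites that differ (all 50 analysed).** Site rates of 70/80/90% give 20%, against 7.6% for a uniform 80%. Site rates of 75/85/95% give 47%, against 20% for a uniform 85%.

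**Step 4: coding of the third answer.** Suppose, for illustration, that 70% prefer KAD, 20% have no preference and 10% prefer no device.

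- KAD versus all other answers: 50 people at p = 0.70, risk 0.8%.
- No-preference answers dropped: 40 people at p = 0.70/0.80 = 0.875, in sites of 14, 14 and 12. Here 0.875^14 = 0.154 and 0.875^12 = 0.201, so the site risk is 1 − 0.846² × 0.799 = 0.43. With the order groups included, the enumeration gives 46%.

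**Step 5: does the remedy work?** In simulated trials on this design at p = 70, 75, 80, 85 and 90%, maximum likelihood diverged in 0.6, 2.6, 7.9, 19 and 46% of 3,000 trials per rate, which agrees with Step 2. Firth-penalised fits were finite in 500 of 500 trials at each rate.

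**The case against.** **The plan does not say maximum likelihood or Wald.** Firth and exact logistic regression both fit its wording, and a likelihood-ratio test stays finite under separation. That is true, so this is an unspecified method rather than a wrong one. But the default reading is the one that fails, and nothing in the text points elsewhere.

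**A reader might infer that a unanimous group is likely whenever KAD is clearly preferred.** The documents do not support this. On a two-sided sign test 33 of 50 (66%) is already significant, and power is 94% at a true 75% and over 99% at 80%. Separation at those rates is 2.6% and 7.6%. The success criterion in section 8.1 is a mean VAS reduction of 10 mm or more, and nothing ties that to a preference near 90%.

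**A reader might also infer that the estimates would be exaggerated even without separation.** That is not shown. The simulations behind such a statement used equal rates in all cells, so the true effects were zero. A check with real site and order effects found the bias small and not consistently away from zero.

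**The preference objective does not need the model.** Secondary objective 2 asks which method subjects prefer, and the objective about location uses VAS. The overall proportion preferring KAD can be estimated with an exact interval whatever happens to the coefficients. This stands and limits the harm, although the plan does not specify that summary either.

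**The coding of the no-preference answer matters more than the estimator.** Step 4 supports this. The coding rule has to come first, and the fix includes it.

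**Conclusion.** The concern holds as a minor point. The plan specifies a model that can lack a finite estimate in groups of 16 to 17 and names nothing to use when it does. With a binary outcome, all 50 analysed and equal rates at every site, the risk is about 1% at 70% preference, 8% at 80%, 20% at 85% and 46% at 90%. With 40 analysed it is about 16%, 33% and 60% at 80%, 85% and 90%. It also rises if sites differ. Because the documents state no expected rate, they do not show which part of this range applies.

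The consequence is confined to the location and order effects on preference. The VAS analyses are not touched. The change is still worth making, because a concrete method that avoids the failure costs one sentence.

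**What to change.** In section 8.4, and in the copies in section 8.2 and the Study Summary:

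1. State how the no-preference answer is coded. One option is KAD versus all other answers, which keeps all 50 people.
2. Specify Firth penalised-likelihood logistic regression with profile-likelihood confidence intervals, or exact logistic regression, with location and order as the two factors.
3. Report the raw counts of all three answers by site and order, and the overall proportion preferring KAD with an exact confidence interval.

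**Cost.** A sentence or two of text, with no new data or subjects. Firth estimates are slightly shrunk towards no effect. Neither method adds information, so a unanimous site will still have a wide interval. Coding KAD versus all other answers counts an indifferent subject as not preferring KAD, which is why the three-way counts should be shown beside the model.

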# 9 Safety and Adverse Events

#### 9.1 Definitions

# 9.1.1 Adverse Event

An **adverse event** (AE) is any symptom, sign, illness or experience that develops or worsens in severity during the course of the study. Intercurrent illnesses or injuries should be regarded as adverse events. Abnormal results of diagnostic procedures are considered to be adverse events if the abnormality:

- results in study withdrawal
- is associated with a serious adverse event
- is associated with clinical signs or symptoms
- leads to additional treatment or to further diagnostic tests
- is considered by the investigator to be of clinical significance

For FDA regulated studies the FDA defines an adverse event as the following:

Adverse event means any untoward medical occurrence associated with the use of a drug in humans whether or not considered drug related.

In this study, the most likely event would be an adverse reaction to lidocaine. In this specific setting, using this dosage of lidocaine the most likely reaction will occur at the local injection site. A systemic reaction would be exceedingly unlikely.

### 9.1.2 Serious Adverse Event

#### **Serious Adverse Event**

Adverse events are classified as serious or non-serious. A serious adverse event is any AE that is:

- fatal
- life-threatening
- requires or prolongs hospital stay
- results in persistent or significant disability or incapacity
- a congenital anomaly or birth defect
- an important medical event

Important medical events are those that may not be immediately life threatening, but are clearly of major clinical significance. They may jeopardize the subject, and may require intervention to prevent one of the other serious outcomes noted above. For example, drug overdose or abuse, a seizure that did not result in in-patient hospitalization, or intensive treatment of bronchospasm in an emergency department would typically be considered serious.

All adverse events that do not meet any of the criteria for serious should be regarded as **non-serious adverse events**.

For additional information on definitions and clarifications which may be helpful in creating the safety monitoring portion refer to Appendix 17.7

#### 9.2 Recording of Adverse Events

At each contact with the subject, the investigator will seek information on adverse events by specific questioning and, as appropriate, by examination. Information on all adverse events will be recorded immediately in the source document, and also in the appropriate adverse event module of the case report form (CRF). All clearly related signs, symptoms, and abnormal diagnostic procedures results should be recorded in the source document, though should be grouped under one diagnosis.

All adverse events occurring during the study period will be recorded. The clinical course of each event will be followed until resolution, stabilization, or until it has been determined that the study intervention or participation is not the cause. Serious adverse events that are still ongoing at the end of the study period will be followed up to determine the final outcome. Any serious adverse event that occurs after the study period and is considered to be possibly related to the study intervention or study participation will be recorded and reported immediately.

# 9.3 Relationship of AE to Study

# 9.4 Reporting of Adverse Events, Adverse Device Effects and Unanticipated Problems

Investigators and the protocol sponsor (which may or may not be a Penn Investigator) must conform to the adverse event reporting timelines, formats and requirements of the various entities to which they are responsible,

If the report is supplied as a narrative, the minimum necessary information to be provided at the time of the initial report includes:

- Study identifier
- Study Center
- Subject number
- A description of the event
- Date of onset

- Current status
- Whether study intervention was discontinued
- The reason why the event is classified as serious
- Investigator assessment of the association between the event and study intervention

Additionally all other events (unanticipated problems, adverse reactions, unanticipated adverse device effects and subject complaints will be recorded and reported with respect to institutional and federal policies as described in the Penn Manual and below.

# 9.4.1 Follow-up report

If an SAE has not resolved at the time of the initial report and new information arises that changes the investigator's assessment of the event, a follow-up report including all relevant new or reassessed information (e.g., concomitant medication, medical history) should be submitted to the IRB. The investigator is responsible for ensuring that all SAE are followed until either resolved or stable.

# 9.4.2 Data and Safety Monitoring Plan

Data and safety monitoring will be performed by the principal investigator. Monitoring will be conducted per the Lidocaine drug label: "Careful and constant monitoring of cardiovascular and respiratory (adequacy of ventilation) vital signs and the patients state of consciousness should be accomplished after each local anesthetic injection." For additional safety precautions, vitals will be also be obtained prior to subject receiving their first injection. Vitals will include heart rate, blood pressure, respiratory rate. Assessment of the participants adequacy of ventilation will also be carried out prior to and after the lidocaine injections.

# 10 Study Administration, Data Handling and Record Keeping

# 10.1 Confidentiality

Information about study subjects will be kept confidential and managed according to the requirements of the Health Insurance Portability and Accountability Act of 1996 (HIPAA). Those regulations require a signed subject authorization informing the subject of the following:

- What protected health information (PHI) will be collected from subjects in this study
- Who will have access to that information and why
- Who will use or disclose that information
- The rights of a research subject to revoke their authorization for use of their PHI.

In the event that a subject revokes authorization to collect or use PHI, the investigator, by regulation, retains the ability to use all information collected prior to the revocation of subject authorization. For subjects that have revoked authorization to collect or use PHI, attempts should be made to obtain permission to collect at least vital status (i.e. that the subject is alive) at the end of their scheduled study period.

# **10.2 Data Collection and Management**

Paper-based records will be kept in a secure location and only be accessible to personnel involved in the study. Paper based records will be input into a secure electronic database and the paper records will be destroyed as soon as is possible.

Computer-based files will only be made available to personnel involved in the study through the use of access privileges and passwords, and will be kept on password-secured computers.

Wherever feasible, identifiers will be removed from study-related information, with subjects assigned unique non-identifiable study IDs.

Each subject will be assigned a random study ID number, and a key will be used to link this number to their identifiable information. This link will be used only to track adverse events if they occur.

Study data, i.e. visual analog scale ratings, preferences, and demographic information will not be connected with names, birth dates, or MRNs at any time. Data will be collected in this manner on paper and will be immediately encoded in a secure computer database, and the paper records will be kept securely until after the closure of the study with the IRB.

Electronic identifiable information will be stored on the Penn Medicine server and that any paper documents with identifiers (such as consent forms) will be stored in a secure location under lock and key.

Data will be kept on password-protected computers.

A resource at the University of Pennsylvania that can assist you in developing and maintaining data collection and management systems is the Clinical Research Computing Unit (CRCU) in the Center for Clinical Epidemiology and Biostatistics (CCEB) Records Retention

# 11 Ethical Considerations

#### 11.1 Risks

The main risk of this study is the (expected) discomfort of lidocaine injection in the face and back. Lidocaine is a well-studied and well-tolerated drug. The risks of injecting this dose of lidocaine (0.5mL, 1%) are exceedingly low. The most likely reaction to this dose will be at the site of the injection. Inadvertent intravenous injection is theoretically possible but has not happened in over hundreds of thousands of injections in our clinic while properly anesthetizing skin for cancer removal since 2005. Furthermore, the concentrations and volume injected has an infinitesimal risk of inducing systemic side effects. Adverse reactions to lidocaine will be treated according to standard of care. Study personnel are also well trained in diagnosing side effects of lidocaine toxicity. There will be no epinephrine used in this study (a common additive to lidocaine) - this lowers the chances of an adverse reaction. There are no known risks from application of a KAD at the peri-injection site. Covino BG: Pharmacology of local anesthetic agents. Br J Anaesth. 58:701-716 1986 Walsh A, Walsh S: Local anesthesia and the dermatologist. Clin Exp Dermatol. 36(4):337-343 2011.

## 11.2 Benefits

Anecdotal evidence claims that local anesthetic injection is the most painful part of minor dermatological procedures. A reduction in the pain of injections by the vibration device would improve the overall patient experience and would be easily generalizable to all patients in the clinic, and possibly patients in outpatient surgical settings. Furthermore, if successful this study would provide evidence based guidelines for the proper use of these medical devices in multiple locations on the body.

# 11.3 Risk Benefit Assessment

We anticipate that the potential benefits and knowledge to be gained by this study outweigh the potential risks to subjects involved in this research study for the following reasons: Individuals have volunteered to participate and given informed consent to enter the study. They face minimal risk. There are no direct benefits for participation in the study. The knowledge gained will benefit those receiving similar injections in the future.

